3.3.3 Neurocognitive/Behavioral Measure Outcomes

We will apply several robust neurocognitive tests to measure the effects of BCG vaccination on mentation, including the MoCA, RBANS, CDR-SB, NPI-Q, HADS, DCT Clock and FAQ.

3.3.4 Structural and Functional MRI Measure Outcomes

Up to 12 participants over 60 years old will be invited to undergo 3T structural and functional MRI at Week 1 and Week 52 visits to assess the effect of the study vaccine on regional brain volumes, cerebral perfusion, brain connectivity, and safety. Each scan will include high-resolution T1-weighted multi-echo MPRAGE for volumetric analysis, task-free blood oxygen level dependent (BOLD) sequence to measure resting neural connectivity, diffusion tensor imaging (DTI) to quantify white matter structural connectivity, T2-weighted fluid attenuated inversion recovery (FLAIR) sequence, and susceptibility- weighted imaging (SWI).

4 SUBJECT SELECTION

Each Investigator must adhere to the protocol detailed in this document and agree that any changes to the protocol must be approved by Institutional Review Board (IRB). Each investigator will be responsible for enrolling only those study subjects who have met protocol eligibility criteria.

4.1 Inclusion/exclusion Criteria

Investigators will use their best clinical judgment when selecting potential research subjects for this study and will not enroll any individuals who are frail or in questionable health, even if they meet all inclusion/exclusion criteria.

4.1.1 **Inclusion Criteria**

Study subjects meeting all of the following criteria will be allowed to enroll in the study:

1. Individuals between the ages of 55-85;
2. MCI or moderate dementia due to AD as defined by the 2011 NIA-AA Workgroup recommendations;
3. MoCA ≥ 8 at screening;
4. Global CDR between 0.5-2 (inclusive) at screening;
5. Amyloid and/or tau biomarkers indicative of AD pathology;
6. Education level, English language skills and literacy indicates subject will be able to complete all assessments;
7. Has a study partner who, in the investigator's judgement, has frequent, direct contact with the participant at least several days a week, can accompany the participant to all visits, and is also able to provide information to study investigator/staff;
8. Willing and able to complete all assessment and study procedures, including blood and lumbar punctures, and clinical assessments;
9. If on cholinesterase inhibitor and/or memantine, doses are stable for 3 months prior to baseline;
10. Negative test results for HIV antibody and Tuberculosis (QuantiFERON or T-spot TB test) at screening;
11. No prior BCG exposure either through birth vaccinations (born in North American) or BCG bladder cancer treatment.

4.1.2 **Exclusion Criteria**

Subjects meeting any of the following criteria during the screening evaluation will be excluded:

1. History of chronic infectious disease, such as HIV or untreated or active hepatitis;
2. History of tuberculosis, positive interferon-gamma release assay (IGRA, also known as the QuantiFERON-TB test) or T-spot TB test, including a test with a high reactivity to mycobacteria of non-tuberculosis variety;
3. Prior BCG vaccination, positive T-spot tuberculosis test or a T-spot test showing significant Mycobacteria exposure;
4. A positive SARS-CoV-2 PCR result within 3 months of screening, or known close contact with a confirmed COVID-19 positive person or symptoms highly suspicious for COVID-19 (per CDC guidelines) within 1 month of screening, including fever, cough, shortness of breath, chills, muscle pain, new loss of taste or smell, vomiting or diarrhea, and/or sore throat, based on clinician's judgment;
5. History of treatment with metformin within the past one year;
6. Treatment with other investigational agents which, at the discretion of the investigator, interfere with safety and/or study outcomes;
7. Current treatment with immunosuppressants (calcineurin inhibitors, corticosteroids, or biological or cytotoxic immunosuppressants, or disease or condition likely to require high dose steroid or

- immunosuppressive therapy);
8. Other conditions or treatments associated with increased risk of infections or treatment with immunosuppressive medications for any reason;
 9. Current treatment with aspirin > 160 mg/day or chronic, daily NSAIDs;
 10. Current (as of time of study screening) or chronic use of antibiotics;
 11. History of keloid formation;
 12. Living with someone who is immunosuppressed and/or at high risk for infectious diseases (for example, HIV+ or taking immunosuppressive medications for any reason), or in a job (e.g. healthcare) in which the subject works with immunosuppressed populations;
 13. Other/confounding neurological or psychiatric condition, unstable medical or psychiatric conditions, contraindications to BCG use and lab abnormalities or concurrent medication use posing risk for BCG or study procedures;
 14. Laboratory abnormalities in B12, Folate, TSH, or other common laboratory parameters that may contribute to cognitive dysfunction per clinician judgment;
 15. Laboratory abnormalities in CBC, electrolytes, LFTs, BUN, Cr, total serum immunoglobulins, ESR, CRP, or urinalysis posing risk to treatment with BCG per clinician judgment;
 16. Laboratory abnormalities in PT-INR, which would pose a risk to performing the lumbar puncture procedure;
 17. Discontinuation of cholinesterase inhibitor or memantine within one month (28 days) prior to baseline visit;
 18. Females who are pregnant, lactating or of child-bearing potential;
 19. If male with female partner(s) of childbearing potential, unwilling or unable to adhere to contraception requirements specified in the protocol.
 20. Increased intracranial pressure as determined on a fundoscopy/neurological examination performed within 30 days of LP;
 21. Administration of live vaccine within 30 days of screening visit or BCG immunizations
 22. Administration of non-live vaccine within 14 days of screening visit or BCG immunizations
 23. If participating in optional MRI: Existing contraindication to MRI per MGH Athinoula A. Martinos Center research guidelines

4.1.2.1 Women of Childbearing Potential (WOCBP)

For the purposes of this study, women of childbearing potential are defined as all women who are capable of becoming pregnant, unless they meet one of the following criteria:

1. 12-months post-menopausal.
2. Post-hysterectomy.
3. Surgically sterile.

If a female subject does not meet these criteria and is considered of childbearing potential, they will be excluded from the clinical trial.

Male subjects with female partners of child-bearing potential must use at least 1 of the following contraceptive methods: hormonal contraceptives (oral, injectable, patch, intrauterine devices), a barrier method (such as condoms or diaphragm) used with a spermicide (a foam, cream, or gel that kills sperm), male sterilization, or total abstinence from heterosexual intercourse, when this is the preferred and usual lifestyle of the subject. Abstinence is defined as refraining from heterosexual intercourse during the entire period of risk associated with the study. Note that periodic abstinence (calendar, symptothermal, post-ovulation methods), withdrawal (coitus interruptus), spermicides only,

and lactational amenorrhoea method are not acceptable methods of contraception.

4.2 Recruitment

Up to twenty five subjects will be screened and enrolled in the study, and after screening we expect 12 subjects to complete the study.

4.2.1 Recruitment of Subjects through Advertising

Advertisement flyers will be posted on bulletin boards around MGB to advertise for the study as well as an advertisement on Partners Rally for Research. A phone number will be provided that will ring directly to the research coordinator, and voice messages can be left for the coordinator on a password-protected voice mailbox. The study coordinator will contact the subject and explain study in further detail and if the subject is interested, potentially complete a telephone prescreening. A listing of the study will also be posted on the MGH ACTRU website.

Subjects may also be recruited through the distribution of IRB approved recruitment materials at community outreach initiatives including informational sessions to various community partners such as city-based and non-profit organizations.

4.2.2 Recruitment of Subjects from the Massachusetts Alzheimer's Disease Research Center

Subjects will also be recruited from an observational study that follows a longitudinal research cohort (LC) of approximately 400 active research participants in the Massachusetts Alzheimer's Disease Research Center (MADRC) recruited from the MGH's Memory Disorders Unit clinic and other diverse sources. LC subjects are followed-up on an approximately annual basis, either in-person at the MGH or by means of a telephone follow-up 'visit'. Study staff will only contact subjects that have indicated to the MADRC that they are interested in hearing about/participating in other studies.

4.2.3 Recruitment of Subjects from among MGB Providers

Subjects will be recruited from the outpatient clinical practices of the principal investigator ([name]). If the potential subject is the investigator's patient, another member of the study or clinic staff will introduce the study to the patient and determine if they are interested in learning more about the study. An NP investigator will be made available to explain the study to the subject at their request. If the potential subject is not the investigator's patient, the investigators will not directly approach the patient regarding possible participation in the study.

Other providers across MGB will also be made aware of the study (including key eligibility criteria) via an IRB-approved email and a link to the Rally ad. These providers (not participating directly in the study) may discuss the study directly with their patients, if they choose to do so. If the prospective participant is interested, their provider will provide them with a link to the Rally ad, which contains the research coordinator's contact information.

4.2.4 Recruitment of Subjects from the CTRU Registry

A research volunteer registry (P2021000916) was established in 2021 to maintain a list of people interested in participating in clinical research with the MGH Clinical and Translational Research Unit (CTRU). The goal of the CTRU, located in CNY 149, is to serve the clinical and research departments, institutes, centers, programs and labs that comprise the MGH Neuroscience community and to be a foundational component and research core facility within MGH's emerging translational programs. Eligible participants who have consented to be contacted for future research may be identified using data stored within the volunteer registry. These participants will be contacted by phone or email and evaluated for interest and eligibility using the study-specific phone screen.

5 SUBJECT ENROLLMENT

5.1 Informed Consent Process

This study will be conducted in compliance with Title 21 Part 50 of the United States of America Code of Federal Regulations (CFR), Federal Regulations, and ICH Guidance Documents pertaining to informed consent.

Potential subjects will be given general information about the research (e.g., through informational sheets, email, online Rally ad, or discussion with their treating physicians). If they are interested in learning more about the study, they will then contact the research coordinator. The research coordinator will obtain verbal consent in accordance with Mass General Brigham's Prescreening Guidelines prior to performing a telephone prescreening interview. Information collected during the telephone prescreen will be entered directly into a REDCap survey for review by clinicians to determine eligibility for the study. If the subject meets pre-screening criteria and wishes to continue the screening process, an in-person screening visit will be scheduled.

At the screening visit, prior to starting the consenting process, one of our licensed Nurse Practitioners, [name], DNP, [name], NP, [name], NP or one of our physicians [name], MD and [name], MD will evaluate capacity to consent. These clinicians are experienced in evaluating capacity to consent in cognitively impaired patient populations and perform this assessment regularly. Like informed consent, evaluation of consent capacity is a process. The consenting clinician begins with an informal conversation prior to the start of the consent discussion with a prospective subject and the study partner, including simple questions to determine if the prospective subject may have problems that could affect decision making.

Following the initial informal discussion, an investigator will discuss with the potential subject and their study partner the details of the study using the informed consent document as a guide. This discussion will include all the required elements of informed consent, including the purpose of the research, the procedures to be followed, the risks and discomforts, as well as potential benefits associated with participation, and alternative procedures to study participation. Their questions will be answered to their satisfaction. The subject will be provided with adequate time to reflect on the potential benefits and risks and possible discomforts of participation, and to make an informed decision. The capacity to consent again is gauged by an experienced licensed clinician investigator during the consent process through an evaluation of the participant's understanding of their condition, their options for treatment, their understanding of the potential benefits and risks of participating in the clinical trial and of their understanding regarding the voluntary nature of their participation in the trial. In addition, participants are evaluated for their level of orientation and understanding of what will happen during the trial. Following this process, a discussion with the participant's study partner will also inform the determination of the patient's capacity to consent. All study staff will report any changes in function of the participant to the investigators, who will then reassess and document any changes in the patient's capacity to consent.

If the clinician determines that the subject has adequate consent capacity, the participant will be able to consent for themselves and may enroll into the study. If it is determined by the clinician that the participant is unable to consent, but is willing and able to assent, then the LAR will provide surrogate consent to enroll the participant in the study. In either case, a study partner is required for participation in the study and they will be required to sign the consent form as such.

Prior to proceeding with surrogate consent for assenting subjects, the clinician will also ensure that the surrogate LAR understands that his or her decisions should be based on "substituted judgment," which means that the decision reflects a potential subject's own views when s/he had the capacity to express them. If a potential subject did not

previously express a view on the matter, the surrogate should make the decision based on the potential subject's best interests.

A licensed Nurse Practitioner Investigator or Physician Investigator will then obtain written informed consent or surrogate consent from each participant prior to the initiation of any study procedures. We have included [name], DNP, [name], NP, and [name], NP as study staff. All are experienced research nurse practitioners who will be consenting participants for this study in addition to the physician investigators. They currently consent on several other IRB-approved interventional trials run by the group, both industry and investigator sponsored. All potential subjects will be given the opportunity to speak with the Physician Investigator should a licensed Nurse Practitioner be involved in obtaining informed consent.

If a participant is deemed unable to consent, either at the start of the extension study or while participating in the study, then consent will be obtained from a legally authorized representative. The relationship of the representative to the subject will be documented and kept for our records. The list of eligible legally authorized representatives, in order of preference, is as follows:

1. Court appointed guardian with specific authority to consent to participation in research or authority to make health care decisions for a class of diagnostic and therapeutic decisions inclusive of the proposed research
2. Health care proxy/person with durable power of attorney with specific authority for making health care decisions inclusive of the proposed research
3. Spouse, adult child, or adult sibling.

Subjects who cannot give informed consent must be able to give assent. If the individual objects to participation, they will not be enrolled. Investigators will document capacity to give assent during the consenting process.

5.2 Remuneration

All subjects will receive:

- Parking fees paid for all in-person visits
- Lunch voucher provided for subject at each study visit that exceeds two hours, which can be used at the cafeteria at MGH CNY 149
- If appropriate, travel expenses will be reimbursed, including mileage at the current IRS travel rate for medical purposes, up to \$150 per visit
- Honoraria: Up to \$540 if subject completes the study (up to \$740 including optional MRIs):
 - \$15 for screening (SVa and SVb, inclusive)
 - \$25 for each subsequent visit to the screening visit (\$125 total)
 - \$100 for each lumbar puncture (\$300 total)
 - \$100 upon study completion

Optional study activities:

- \$100 for each optional MRI (\$200 total)

If for any reason the subject stops the study, they will be compensated for only the visits that they have completed.

Payment will be made in the form of a check mailed to the subject's home address. They should receive the check within 2-3 weeks from the date of the study visit or study completion. Their social security number (SSN) will be required to process the payments.

An Open Label Trial to Evaluate the Effects of BCG Immunization on Biomarkers of Inflammation/Immune Response and Alzheimer's Disease in Adults with Mild Cognitive Impairment and Mild-to-Moderate Dementia due to Alzheimer's Disease
Version Date#: October 13, 2022/Version 3.3

5.3 Discontinuation

5.3.1 Study Discontinuation

A study subject will be discontinued from participation in the study if:

1. Any clinical adverse event (AE), concurrent illness, or other medical condition or situation occurs such that continued participation in the study would not be in the best interest of the subject.
2. The subject meets any exclusion criteria (either newly developed or not previously recognized) and/or fails to continue to meet inclusion criteria which the study physician deems to be a risk to continued participation.

5.3.2 Discontinuation of Study Intervention

Individual subjects will be allowed to continue in the study, but administration of the second immunization will be withheld if, after the first injection, any of the following criteria are met:

1. Any of the following serious adverse events attributable to BCG:
 - Life-threatening adverse event
 - Permanent or severe disability
 - Important BCG-specific medical events that do not result in death, are not life-threatening, and/or do not require hospitalization will be considered as serious if, based on appropriate medical judgment, they jeopardize the participant and would require medical or surgical intervention to prevent a serious adverse event.
2. Presentations of symptoms of disseminated BCG infection including persistent fevers, night sweats, weight loss. These symptoms may not occur within the timeline of the current study (they usually present 4 months to 2 years after vaccination), however should such symptoms occur prior to the second immunization, the study vaccine would be stopped.
3. The occurrence of any serious local skin reactions (\geq grade 3 ulceration, abscess formation, skin necrosis at the site of injection, or the development of suppurative lymphadenitis) as characterized by the standard FDA Toxicity grading scale (<https://www.fda.gov/regulatory-information/search-fda-guidance-documents/toxicity-grading-scale-healthy-adult-and-adolescent-volunteers-enrolled-preventive-vaccine-clinical>).

5.3.3 Voluntary Withdrawals

A participant may choose to discontinue participation in the study at any time. Participants may be asked to complete an Early Termination Visit when they withdraw consent, i.e. withdrawing consent for participation in future study procedures.

5.3.4 Lost to follow-up

The following actions must be taken in relation to a subject who fails to attend the clinic for a required study visit:

- The site must attempt to contact the subject and re-schedule the missed visit as soon as possible.
- The site must counsel the subject on the importance of maintaining the assigned visit schedule and ascertain whether or not the subject wishes to and/or should continue in the study.
- In cases where the subject is deemed 'lost to follow up', the Investigator or designee must make every effort to regain contact with the subject (where possible, 3 telephone calls and, if necessary an email with read receipt). These contact attempts should be documented in the subject's study record.
- Should the subject continue to be unreachable, only then will he/she be considered to have

withdrawn from the study with a primary reason of “Lost to Follow-up”.

5.4 Early Termination Visit (ET)

Subjects who decide to withdraw from the study at any point after receiving the initial BCG injection may be invited to come in for an Early Termination Visit.

5.5 Termination of Study

This study may be prematurely terminated if, in the opinion of the investigator, there is sufficient reasonable cause.

Circumstances that may warrant termination include, but are not limited to:

1. Determination of unexpected, significant, or unacceptable risk to subjects;
2. Unsatisfactory enrollment;
3. Insufficient adherence to protocol requirements;
4. Data that are not sufficiently complete and/or evaluable;
5. If any grade 3 “severe” or higher adverse event occurs in seven or more participants, or if any participants have severe systemic reactions to the antigenicity of the vaccination with respiratory problems, the study protocol will be paused for review. The FDA, and all other relevant oversight bodies will be notified in a timely fashion if a batch of BCG is problematic.
6. If during the study any subject develops a systemic BCG infection in the absence of an underlying immunocompromised state, the study will be stopped for a study of this side effect.

If the study is prematurely terminated or suspended, the investigators will promptly inform the institution and regulatory authorities of the termination or suspension and the reason(s) for the termination or suspension. The IRB will also be informed promptly and provided the reason(s) for the termination or suspension by the investigator, as specified by applicable regulatory requirement(s).

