BCG, a highly safe, live, attenuated vaccine used throughout the world to prevent tuberculosis and confers many health-promoting non-specific effects, from preventing infectious disease to treating cancers. These effects rely on its induction of trained and heterologous immune responses in the host. Such immune effects directly overlap and influence immune responses known to occur in CNS disease; non-human studies have found benefit to BCG vaccination on models of Parkinson's and Alzheimer's diseases, including cognitive improvement. These studies provide the impetus for our initiating clinical trials with BCG oriented towards primary prevention of AD in older adults or disease modification and secondary or tertiary prevention in adults whom AD pathological changes are already in motion. This pilot study initiates this program, with focus on the immune consequences of treatment and potential changes in AD-specific biomarkers and cognition after vaccination. The BCG strain used in this study is not approved in the US for immunization against tuberculosis or for the treatment of AD.

A pilot, open-label study of BCG immunization (Protocol#2020P002042) in both healthy older adults and adults with Mild Cognitive Impairment is currently underway with a focus on the immune consequences of BCG vaccine and potential changes in AD-specific biomarkers and cognition after vaccination. The 3-month, open-label study has so far demonstrated that repeated administration of BCG vaccine is safe and tolerable in healthy adults and adults with mild cognitive impairment between the ages of 55 and 80 years old. Following two intradermal vaccinations to participants in the unblinded study, there have been no serious adverse events, no clinically significant abnormalities detected in safety lab (eg. metabolic, hematologic, and immune labs) or vital sign measurements, and only mild-to-moderate, expected adverse events related to the lumbar puncture and blood draw procedures in the protocol. This small-scale study has informed the trial design and validated the assays included in the proposed in this protocol.

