11.3.6 Adverse Events and Serious Adverse Events - Reportable Events

All events that meet the above criteria for Serious Adverse Events must be reported to the IRB within 24 hours of a study investigator being notified of the event.

Any adverse reaction that is serious, unexpected, and associated with the use of the product will be reported to the FDA in an IND safety report no more than 15 calendar days after the PI determines that the suspected adverse reaction qualifies for reporting, or 7 days for unexpected fatal or life-threatening adverse reaction reports.

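### Outside two one-participant triggers, the only fixed study-level pause count for serious BCG reactions is seven participants with a Grade 3+ event of any cause, too high to protect a trial of about 15

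*Combined protocol and SAP*

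**What the plan says.** Section 5.5 lists circumstances that may lead to termination. Items 1 to 4 carry no number; item 1 covers unexpected, significant or unacceptable risk and rests on the investigator's opinion, and the list is stated not to be exhaustive. Under item 5 the study is paused for review if any Grade 3 "or higher adverse event occurs in seven or more participants, or if any participants have severe systemic reactions" with respiratory problems. Item 6 stops the study if one participant without immunocompromise develops a systemic BCG infection.

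Section 5.3.2 acts on the individual: "administration of the second immunization will be withheld if, after the first injection, any of the following criteria are met". Its criteria include BCG-attributable life-threatening or disabling events and, as item 3, "The occurrence of any serious local skin reactions", meaning Grade 3+ ulceration, abscess, necrosis or suppurative lymphadenitis. Section 5.3.1 removes a participant when "continued participation in the study would not be in the best interest of the subject". Under section 11.3.6, serious adverse events "must be reported to the IRB within 24 hours of a study investigator being notified of the event", and a serious, unexpected, product-associated reaction "will be reported to the FDA in an IND safety report no more than 15 calendar days after the PI determines" that it qualifies, or within 7 days if fatal or life-threatening.

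On size, section 3.1 allows up to 25 enrolled, section 6.2.1.3 treats anyone who signs consent as enrolled, section 8.1 plans about 15, and section 4.2 expects 12 to complete.

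**The concern.** The trial gives two doses of a live vaccine to adults aged 55 to 85 with MCI to moderate dementia, some enrolled by surrogate consent, and safety is its first primary objective. The protocol treats one Grade 3+ local reaction as serious enough to withhold that person's second dose, yet sets no low count at which dosing of everyone else is paused. One BCG-related death outside the two named triggers, or up to six related serious reactions, could occur without any fixed rule requiring a pause. The decision would then fall to open-label investigators who also judge seriousness and causality.

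Item 5 is also unclear on whether seven means any Grade 3+ event in seven people or the same event in seven people. The second reading would make the rule harder still to reach.

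**Working it through.** **Inputs.** Count of seven (5.5 item 5). Sizes: about 15 planned (8.1), a ceiling of 25 (3.1) and 12 expected completers (4.2). Severe cutaneous reaction rates of 0.02% after the first dose and 0.04% after the second (9.1). The documents give no derivation for seven, no expected Grade 3+ rate and no accrual rate, so there is no figure to reproduce. The rates of 1% to 40% below are assumptions.

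**Step 1: shares.** 7/15 = 46.7%. 7/25 = 28.0%, which is a floor for the vaccinated group because the 25 includes screen failures. 7/12 = 58.3%.

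**Step 2: chance of ever reaching seven.** With X binomial(n, p), P(X ≥ 7) = Σ(k = 7 to n) C(n,k) p^k (1−p)^(n−k).

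| All-cause Grade 3+ rate p | n = 12 | n = 15 | n = 25 |
|---|---|---|---|
| 10% | 0.0001 | 0.0003 | 0.010 |
| 20% | 0.004 | 0.018 | 0.220 |
| 30% | 0.039 | 0.131 | 0.659 |
| 40% | 0.158 | 0.390 | 0.926 |

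Solving P(X ≥ 7) = 0.5 gives p = 0.540 (n = 12), 0.435 (n = 15) and 0.263 (n = 25).

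**Step 3: the count is all-cause, so unrelated events help reach it.** Suppose 20% have an attributable severe event and 12.5% independently have another. Then p = 1 − (0.80)(0.875) = 0.30, and seven is reached with probability 0.13 (n = 15) or 0.66 (n = 25). With 10% attributable, p = 1 − (0.90)(0.875) = 0.2125, giving 0.02 or 0.27.

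**Step 4: a low count of related events.** At the 9.1 rates, p = 1 − (1 − 0.0002)(1 − 0.0004) = 0.0006 per two-dose participant, and P(X ≥ 2) = 0.00004 (n = 15) or 0.0001 (n = 25). At assumed attributable rates:

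| Rate | Count | n = 12 | n = 15 | n = 25 |
|---|---|---|---|---|
| 5% | two | 0.12 | 0.17 | 0.36 |
| 5% | three | 0.02 | 0.04 | 0.13 |
| 10% | two | 0.34 | 0.45 | 0.73 |
| 10% | three | 0.11 | 0.18 | 0.46 |
| 20% | two | 0.73 | 0.83 | 0.97 |
| 20% | three | 0.44 | 0.60 | 0.90 |

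For example, at n = 15 and 5%: 1 − 0.95^15 − 15(0.05)(0.95^14) = 1 − 0.463 − 0.366 = 0.171. The n = 25 column is an upper bound, since fewer than 25 may be vaccinated.

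**Step 5: one related death or life-threatening event.** The documents give no rate for such events outside the existing one-participant triggers. If 1% had one (assumed), 1 − 0.99^n = 0.11 (n = 12), 0.14 (n = 15) or at most 0.22 (n = 25). For both added rules together, with a count of two and 5% attributable of which 1 percentage point is fatal or life-threatening: 1 − [0.95^n + n(0.04)(0.95^(n−1))] = 0.19, 0.24 or at most 0.43.

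**The case against.** The protocol is not without safeguards, and a reader who inferred that nothing happens until seven people are harmed would be wrong. Item 1 and the open-ended list let the investigator stop at any time. Individual discontinuation and withholding of the second dose operate from the first event. Besides the 24-hour and 15- or 7-day reports, section 11.3.1.1 sends all adverse events to the IRB after review by the principal investigator, and section 11.3.1 routes unanticipated problems to the institution's review committee. All of this stands, but none of it fixes the number of reactions at which a pause must follow.

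Nor do the documents support reading the 5% to 20% rates as expected. Section 9.1 implies roughly 0.06% per two-dose participant, although its reaction category only approximates the Grade 3+ reactions in 5.3.2. The pilot is reassuring: "The 3-month, open-label study has so far demonstrated that repeated administration of BCG vaccine is safe and tolerable", and "there have been no serious adverse events". Its limit is scope, namely 3 months in healthy and MCI participants aged 55 to 80, while section 9.1 says serious local reactions may appear up to 5 months after vaccination.

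That same delay limits what a pause can prevent. Both doses are given within 28 to 42 days, and the probabilities above are for ever reaching a count, including after dosing has ended. Doses spared cannot be computed without an accrual rate. Finally, choosing two over three is judgement; the documents select neither. These points limit the size of the benefit, but they do not make seven a workable trigger at this sample size.

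**Conclusion.** The point holds, and the rule should be changed. Beyond a respiratory systemic reaction and systemic BCG infection without immunocompromise, the only fixed study-level count is seven all-cause Grade 3+ participants. That gives little protection: an even chance of a pause needs about 43% of 15 participants, or 26% of 25, to have a severe event. A pause after one related death, or after several related serious reactions, depends on discretion.

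The conclusion about seven rests only on the stated count and sample sizes, with independent participants. The comparison with lower counts rests on assumed attributable rates. The documents do not show that such reactions are likely, that two is the correct count, or how many doses a pause would spare. No efficacy or biomarker analysis is affected.

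**What to change.** Add to section 5.5 item 5 that the study is also paused for review:

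- (a) after one death or life-threatening event judged possibly, probably or definitely related to the BCG product; and
- (b) when two participants (three is a reasonable alternative) have had a Grade 3+ local reaction of a type in 5.3.2 item 3, or another serious adverse event, judged related on the same scale, with onset after either BCG dose, including a first dose given in the earlier randomized trial (6.1.1).

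State that relatedness here means the relationship to investigational product recorded under 11.3.5, not to lumbar puncture or other procedures. Keep both one-participant triggers and the all-cause count of seven, and state that the latter counts participants with any Grade 3+ event. Keeping it matters because attribution is judged by open-label investigators.

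The cost is one paragraph in an amendment. No new visits, data or committee are needed, since severity, onset date and relationship are already recorded. The downside is an earlier review pause. For part (b) this is about 0.0001 or less at the 9.1 rate. At an assumed 5% attributable rate it is 0.12 to 0.17 with a count of two (n = 12 to 15; at most 0.36 at n = 25), or 0.02 to 0.04 with a count of three (at most 0.13). A count of three therefore causes fewer pauses at 5%, but at 20% and n = 15 it lowers the chance of a pause from 0.83 to 0.60.
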